5.3 Recruitment: Consort flow will include as per protocol-

Patients will be assessed for eligibility >>>randomization will be done for eligible participants >>> Allocation of treatment in two groups (one arm will be given convalescent plasma with standard medical treatment and another arm will be given standard medical treatment only) >>> follow up till 28 days.

5.4 Withdrawal/ Follow-up: Withdrawal is not expected, follow up till 28 days in all enrolled patient.

5.5 Baseline patient characteristics: following variables will be considered:

- Age at screening (years) = date of screening.
- Time from initial admission to randomization(days) = date of transfusion allotment by snooze method and transfusion of plasma.
- O₂ saturation at baseline.
- PiO₂/FiO₂ ratio at baseline.
- Respiratory rate at baseline.
- Need of Mechanical ventilation at baseline.
- SOFA score at baseline.
- For those who died: Date of death – transfusion start date or date of randomization.
- For those who are alive: Date of last follow-up – transfusion start date or date of randomization.

Section 6:

Analysis

6.1 Outcome definitions:

6.1.1 Definition of primary endpoint: Time to clinical improvement (Clinical improvement: Reduction of two points in ordinal scale or live discharge from the intensive care unit, whichever is earlier)

6.1.2 Secondary endpoints:

1. The proportion of patients in each category according to the ordinal scale at 48 hours and day 7, 14, and 28 after randomization
2. Duration of oxygen therapy
3. Duration of hospital stay
4. The proportion of patients on mechanical ventilation at day 7. (after randomization)
5. Mortality at day 7 and day 28 (after randomization)
6. Duration of Intensive Care Unit stay
7. Incidence of adverse effects in both groups
8. Presence of antibodies against SARS-CoV-2 in serum after plasma administration.
9. Cytokines and acute phase reactants

6.2 Analysis methods:

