Continuous variables will be expressed as mean (SD) or median (range) and compared by Student's t-test or Mann-Whitney U test as appropriate. The categorical data will be analyzed using Chi-Square or Fisher's exact test. To compare pre and post values, a paired t-test or Wilcoxon signed-rank test will be used. To find out the predictor in survival analysis Cox-proportional hazard regression analysis will be applied. The actuarial probability of survival will be calculated by the Kaplan-Meier graph and compared by the log-rank test. The p value < 0.05 will be considered statistically significant.

6.3 Missing data: Not expected, if data are, we will try to impute.

6.4 Additional analyses: Not planned, if required an appropriate analysis will be carried out.

6.5 Harms: The risks will be the same as the risks related to the transfusion of Plasma Components, which are described below in the table. No additional risks of transfusing Convalescent plasma (CP) therapy are expected as a part of enrolment in this study as per previous literature available. The patient will be managed according to the standard of care at treatment centre. All the adverse transfusion events will be recorded and managed by clinicians or investigators as per standard treatment. Risk of Transfusion transmitted Infections (TTI) like transmission of HIV, Hepatitis B and Hepatitis C, Syphilis, and Malaria are very rare due to standard TTI testing of plasma donors at ILBS, New Delhi as per Drug and Cosmetics Act and Rules.

6.6 Statistical software: All statistical tests will be performed using SPSS for Windows version 22 (SPSS IBM Corp. Ltd. Armonk, NY).

6.7 Important references:

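### The primary endpoint is time to clinical improvement, but the SAP's only derived event time ends at death or last follow-up, its log-rank sentence is worded for survival, and no rule covers death before improvement

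*SAP*

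**What the plan says.** - **Primary endpoint (2.2.1, 6.1.1).** The later section reads "Definition of primary endpoint: Time to clinical improvement (Clinical improvement: Reduction of two points in ordinal scale or live discharge from the intensive care unit"; the first of the two to occur counts, and 2.2.1 adds a Day 28 time frame. Death is category 6 of the six-point scale, the worst state.
- **Time-to-event methods (3.5.4, repeated in 6.2).** "The actuarial probability of survival will be calculated by the Kaplan-Meier graph and compared by the log-rank test". For regression: "To find out the predictor in survival analysis Cox-proportional hazard regression analysis will be applied". Neither sentence names an event or a censoring rule.
- **Derived times (5.5).** "For those who died: Date of death – transfusion start date or date of randomization" and "For those who are alive: Date of last follow-up – transfusion start date or date of randomization". No derived time ends at the date of improvement.
- **Sample size (3.3).** Medians of 24 days on standard treatment and 18 on plasma are labelled as survival, and the shorter time is presented as the gain. The result is 190 per arm, and 400 were enrolled.
- **Deaths elsewhere.** Mortality at days 7 and 28 is a secondary endpoint (6.1.2). Section 6.3 expects no missing data and would try to impute any; it does not address death before improvement.

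**The concern.** An SAP has to fix three things for its primary time-to-event endpoint: which date ends the clock, who is censored and when, and what happens to patients who can no longer have the event. This SAP fixes none of them for improvement. What it does write down fits a different endpoint.

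The population has severe COVID-19 and may be ventilated, so deaths before improvement are foreseeable. If they are censored on the date of death, they leave the risk set as though they might still have improved later. The curve then overstates recovery, and the comparison does not count a death as a failure to improve. The trial is open-label, so leaving the choice unwritten also allows it to be made after outcomes are known.

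**Working it through.** **1. What the plan's own figure refers to.** Inputs from 3.3: medians 24 and 18 days, z-values 1.96 and 0.84. If times are exponential, the ratio of improvement rates is 24/18 = 1.333. Events per arm = 2 × (1.96 + 0.84)² / (ln 1.333)² = 189.5, that is 190, which matches the SAP. The calculation makes sense only for time to improvement: read as survival, a fall from 24 to 18 days would mean that plasma shortens life.

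**2. Literal reading: the event is death.** The SAP gives no mortality, so control-arm values are assumed. With 200 per arm and a mortality hazard ratio of 0.75, plasma mortality is 1 − (1 − m)^0.75, where m is control mortality.

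| Assumed control deaths by Day 28 | Expected deaths, both arms | Log-rank power |
|---|---|---|
| 10% | 35 | 13% |
| 20% | 71 | 23% |
| 30% | 107 | 32% |
| 40% | 144 | 41% |

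**3. Loose reading: the event is improvement, and the clock stops at death.** Take a control improvement hazard λ₁ = ln 2/24 = 0.0289 per day and an assumed constant death hazard λ₂.

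- True proportion improved by Day 28 = λ₁/(λ₁+λ₂) × (1 − exp(−28(λ₁+λ₂))).
- Proportion dead without improvement: the same expression with λ₂ in the numerator.
- With deaths censored, 1 − KM estimates 1 − exp(−28λ₁) = 55.5%, whatever λ₂ is.

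| λ₂ per day | Dead by Day 28 | Truly improved | 1 − KM | Overstatement (unrounded values) |
|---|---|---|---|---|
| 0.0075 | 13.2% | 50.7% | 55.5% | 4.7 points |
| 0.015 | 24.2% | 46.6% | 55.5% | 8.9 points |
| 0.02 | 30.5% | 44.1% | 55.5% | 11.4 points |

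**4. Effect on the log-rank test.** Simulated trials, 200 per arm, constant independent hazards, two-sided 5%. Repeat runs differ by a point or two.

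| Improvement hazard ratio | Death hazards, control vs plasma | Rejects, deaths censored | Rejects, deaths held event-free to Day 28 |
|---|---|---|---|
| 1.33 | 0.0075 vs 0.0075 | 57% | 54% |
| 1.33 | 0.015 vs 0.015 | 55% | 50% |
| 1.33 | 0.0075 vs 0.015 | 56% | 23% |
| 1.00 | 0.0075 vs 0.015 | 5% | 12%, nearly all against plasma |

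In the third row the true Day 28 figures are 51% improved and 13% dead on control, and 56% improved and 22% dead on plasma. In the fourth row they are 51% and 13% on control, and 47% and 24% on plasma.

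**The case against.** Four points weigh on the other side.

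- **Loose wording.** Section 3.3 already uses survival for a time where shorter is better, so the Kaplan-Meier sentence may mean improvement too. The date lines sit in a list of baseline characteristics, 6.2 does not refer to them, and they would serve the mortality endpoint. A reader might infer that the SAP definitely puts its primary test on mortality. The text permits that reading but does not establish it.
- **Censoring is implied, not stated.** No sentence censors deaths, and holding them event-free to Day 28 is neither written nor excluded. Censoring at death is also a valid test of the cause-specific improvement hazard, and the 5% rejection at equal improvement hazards is its correct type I error.
- **The plan does not ignore deaths.** Day 28 mortality and the Day 28 ordinal categories are secondary endpoints, and 6.2 gives chi-square or Fisher tests for categorical data. With deaths of 13% vs 24%, a chi-square test on Day 28 mortality rejects in about 82% of simulated trials. A reader might infer that a mortality difference would go unseen; the secondary endpoints show otherwise.
- **The large contrast is conditional.** 56% against 23% requires plasma to double the death hazard. The 56% is not a false-positive rate, because plasma does improve more patients there.

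All four stand, and they limit the size of the point. They do not supply what is missing: an event date, a censoring rule and a rule for death before improvement.

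**Conclusion.** The point holds in this form: the SAP does not tie its log-rank test to its primary endpoint and does not say how death before improvement is handled. Followed literally, it tests mortality, with 13% to 41% power under the assumptions above. Followed loosely, its derived time implies censoring at death, and the curve overstates Day 28 improvement by about 5 to 11 points at assumed deaths of 13% to 31%.

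The effect on the test is small when death hazards are equal (3 to 5 points of power) and large only when mortality differs between arms. All death rates are assumptions, and the model uses constant, independent hazards in otherwise identical patients. It therefore does not support the stronger inference that a treatment which selectively kills slow improvers would look beneficial; that was not modelled. The gap should be closed before the primary analysis is run.

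**What to change.** Add to 6.1.1 and 6.2:

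1. Time runs from randomisation to the first two-point reduction or live ICU discharge, whichever is earlier. Section 5.5 leaves the origin open between transfusion start and randomisation; the control arm has no transfusion, and 6.1.2 already counts its dated endpoints from randomisation.
2. Patients who die without improvement stay in the risk set, event-free, to Day 28.
3. Survivors without improvement are censored at Day 28, or at last contact if lost earlier.
4. Arms are compared by log-rank on these times, with a plot of the cumulative incidence of improvement.
5. The time to death or last follow-up in 5.5 is used for mortality only and moved out of baseline characteristics.
6. The cause-specific analysis, censoring at death, is reported as a sensitivity analysis.

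The cost is a few sentences and one derived variable; the log-rank comparison runs in SPSS 22, which the SAP names. One downside needs a sentence of explanation: the hazard ratio becomes a subdistribution-type ratio, which mixes the effect on improvement with the effect on death.
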